#### 11.1.8. Adverse Event Outcome Classification

Outcome of the event will be defined according to the following:

- Fatal: If death was possibly, probably, or causally related to the event
- Not recovered / not resolved: Subject has exited the study and the AE is ongoing and not expected to resolve
- Recovered / resolved: The event has fully resolved prior to study exit

MDT18010ILSBA Version 4.0 26-SEP-2019 Pag

Page 37 of 50

- Recovered / resolved with sequelae: The event has resolved prior to study exit, but retained pathological conditions resulting from the prior disease or injury
- Recovering / resolving: The subject has exited the study and the AE is ongoing but expected to resolve
- Unknown: The subject has exited the study and the AE outcome is unknown

## 11.2. Reporting of Adverse Events

Assessment of the occurrence of an AE will be based on changes in the subject's physical examination, laboratory results, and/or signs and symptoms. AEs will be monitored until a subject completes the study. Any unresolved procedural- or device-related events that are still ongoing past study exit will be monitored by the physician per their institutional standard-of-care. AEs will be documented in the applicable source documentation and reported on an AE eCRF. To the extent possible, the event to be recorded and reported is the event diagnosis as opposed to event outcome (e.g. death) or symptoms (e.g., fever, chills, nausea and vomiting in the presence of a clinically diagnosed infection is to be reported as infection only).

The following should not be considered an AE:

- A condition requiring a preplanned procedure unless the condition worsened since enrollment
- A preexisting condition found as a result of screening, unless the condition has worsened since enrollment.

#### 11.2.1. Notification to Authorities

The following events are generally considered reportable during the course of this study and should be reported within the timeframes outlined in **Table 2**:

- any AE or SAE related to the Emprint™ Ablation Catheter Kit with Thermosphere™ Technology, accessory devices, or study procedures
- any Device Deficiency
- new findings/updates in relation to already reported events.

MDT18010ILSBA Version 4.0 26-SEP-2019

Page 38 of 50

Table 2. Reporting of Adverse Events

Туре	Report to	Reporting Timeframe (from time of learning of event)
Device Deficiency	Sponsor	Recommended within 10 working days
AE	Sponsor	Recommended within 10 working days
	EC/IRB	Per EC/IRB reporting requirements
SAE	Sponsor	Not to exceed 10 working days
	EC/IRB	Per EC/IRB reporting requirements

Events will be reviewed by sponsor or designee to determine any sponsor reporting obligations to Regulatory Authority and EC/IRB. All applicable events will be reported to Post-Market Vigilance (PMV) by sponsor clinical team; and PMV will also report to Regulatory Authorities when applicable.

AEs will be recorded on the Adverse Event CRF.

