# 6. Study Design

This is a prospective, single-arm, multicenter, non-randomized study. Up to 3 sites in up to 3 countries/regions will enroll up to 30 subjects in total. The study is designed to characterize the safety and performance of the bronchoscopic ablation procedure using the Emprint™ Ablation Catheter Kit with Thermosphere™ Technology.

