#### 6.1. Duration

Assessments will occur at baseline, during and immediately post-procedure, and at 1-month follow-up.

The expected duration of each subject's participation in the study from the baseline visit to the 1-month follow-up is up to approximately 2 months (based on a baseline visit a maximum of 30 days preprocedure and a follow-up window up to 40 days post-procedure).

Based on the expected enrollment rate of 1 subject per site per month, the total duration of the study from first subject enrollment to last subject follow-up is expected to be approximately 18 months.

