# 9.10. Deviation Handling

No written waivers from the CIP will be granted. The Principal Investigator must make every effort to follow the CIP, unless the deviation is necessary in an emergent situation to protect the rights, safety and/or well-being of the subject. Deviations from the CIP will be collected on a Protocol Deviation CRF and reviewed with the Principal Investigator to ensure compliance.

The investigator must notify Medtronic and the reviewing ethics committee (EC) / institutional review board (IRB) of any deviation from the Investigational Plan when specific to the protection of the life or

MDT18010ILSBA

Version 4.0

26-SEP-2019

Page 29 of 50

physical well-being of a subject in an emergency. Such notice must be given as soon as possible, but in no event later than five (5) working days after the emergency has occurred. All study deviations will be reported by Medtronic to the Regulatory Authority (if applicable) via either Final Clinical Study Report or separate notification in case of substantial CIP deviation, for which the Regulatory Authority approval is required before its implementation.

If a pattern of non-compliance is noted, the study manager will determine the course of action to take, such as root cause, review relevant CIP procedures and as applicable retrain and verify understanding of the issue in question. This will be documented in the Study Master Files. In the case of repeated or serious non-compliance, the Sponsor reserves the right to disqualify the offending site.

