#### 11.1.2. Serious Adverse Event (SAE)

For the purposes of this study, a Serious Adverse Event (SAE)\* is an AE that has

- 1. Led to death,
- 2. Led to serious deterioration in the health of the subject, that either resulted in
  - a. A life-threatening illness or injury, or
  - b. A permanent impairment of a body structure or a body function, or
  - c. In-patient or prolonged hospitalization, or
  - d. Medical or surgical intervention to prevent life-threatening illness or injury or permanent impairment to a body structure or a body function.

MDT18010ILSBA

Version 4.0

26-SEP-2019

Page 34 of 50

3. Led to foetal distress, foetal death or a congenital abnormality or birth defect

NOTE 1: This includes device deficiencies that might have led to an SAE if a) suitable action had not been taken or b) intervention had not been made or c) if circumstances had been less fortunate. These are handled under the SAE reporting system.

NOTE 2: Planned hospitalization for a pre-existing condition, or a procedure required by the clinical investigational plan, without serious deterioration in health, is not considered an SAE.

\*For the purposes of this clinical study, SAE definitions will be ISO 14155:2011 compliant with the following exception: only those SAEs that are related to the Emprint™ Ablation Catheter Kit with Thermosphere™ Technology, accessory devices, or study procedures will be captured and reported.

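### A site may take up to 10 working days to tell the sponsor of a related SAE, no shorter than the time recommended for a non-serious AE, and Table 2 does not carry over the rule for near-miss device deficiencies

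*Protocol*

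**What the plan says.** Protocol 11.2.1, Table 2, sets the times for reports from site to sponsor. For an SAE the entry is "Not to exceed 10 working days". For a non-serious AE and for a device deficiency it is "Recommended within 10 working days". The column heading starts the clock when the site learns of the event: "Reporting Timeframe (from time of learning of event". There is no separate row for deaths, serious adverse device effects or unanticipated serious adverse device effects.

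Protocol 9.10 deals with a departure from the plan made to protect a subject's life or physical well-being in an emergency. The investigator must notify the sponsor and the EC/IRB as soon as possible, and "in no event later than five (5) working days after the emergency has occurred".

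Protocol 11.1.2 NOTE 1 extends the SAE definition to device deficiencies that might have led to an SAE in less favorable circumstances, and says of them: "These are handled under the SAE reporting system". The Adverse Event Reference List (Appendix 17.5) repeats the note. Table 2 has a single device-deficiency row and does not refer to it.

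On oversight, section 12 provides for no Data Monitoring Committee and no Clinical Events Committee. Section 11.1 has an independent medical monitor adjudicate related events. Table 2 also sends SAEs to the EC/IRB on that body's own timetable, and section 14.1 applies local requirements and any that an EC/IRB or authority adds.

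**The concern.** The sponsor is the party placed to see events from every site, and with no monitoring committee its review is the main cross-site check. Under 11.2.1 that review, and the sponsor's assessment of its duties to authorities, follows the site's report. Until the report arrives, the other sites may go on treating subjects unaware of the event.

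This matters more because bronchoscopic safety is what the study is meant to characterize. Section 6.2 says that the catheter's CE mark rested on equivalence to the percutaneous antenna, and the human lung data it cites are percutaneous.

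Two features of Table 2 stand out. Seriousness changes the force of the deadline but not its length. And a site with a near-miss device deficiency finds a mandatory limit by way of 11.1.2 but only a recommendation on the row of Table 2 that names device deficiencies.

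**Working it through.** **The windows side by side**

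| Report to sponsor | Length | Force | Clock starts |
|---|---|---|---|
| Non-serious AE (Table 2) | 10 working days | recommended | on learning of the event |
| Device deficiency (Table 2) | 10 working days | recommended | on learning of the event |
| SAE (Table 2) | 10 working days | mandatory | on learning of the event |
| Emergency deviation (9.10) | 5 working days | mandatory | at the emergency |

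The SAE limit is as long as the recommended AE time and 10/5 = 2 times the emergency-deviation limit. Because its clock starts on learning, the delay counted from the event itself can exceed 10 working days.

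**Inputs for the size of the exposure**

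- Enrollment: "expected enrollment rate of 1 subject per site per month" (6.1), at up to 3 sites.
- Sample: the sites "will enroll up to 30 subjects in total" (section 6).
- Total duration, with follow-up as late as day 40: "is expected to be approximately 18 months" (6.1).
- Assumptions not in the documents: 10 working days = 14 calendar days, 5 working days = 7, a month = 30.44 days, Poisson enrollment, and a site that uses the whole window.

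The protocol states no exposure figure to reproduce. Its rate and duration do differ: 30 subjects at 3 per month take 10 months, or 11.3 with 40 days of follow-up, not 18. A staggered site start could explain this. I therefore use two rates:

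- Stated rate: 3 sites × 1 = 3 per month.
- Rate implied by 18 months: 30 / (18 − 40/30.44) = 30 / 16.69 = 1.80 per month.

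The reporting site already knows of its own event. A stricter count therefore takes only the other two sites, which is two thirds of each rate if the sites enroll equally: 2 and 1.20 per month.

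**Formulas**

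Expected further subjects m = monthly rate × calendar days / 30.44. Chance of at least one = 1 − exp(−m).

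Example: m = 3 × 14/30.44 = 1.38, and 1 − exp(−1.38) = 0.75.

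| Count | Rate per month | 10 working days: m, chance | 5 working days: m, chance |
|---|---|---|---|
| All 3 sites, stated rate | 3 | 1.38, 75% | 0.69, 50% |
| All sites, 18-month rate | 1.80 | 0.83, 56% | 0.41, 34% |
| Two unaware sites, stated rate | 2 | 0.92, 60% | 0.46, 37% |
| Two unaware sites, 18-month rate | 1.20 | 0.55, 42% | 0.28, 24% |

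Halving the window halves m in every row. The chance of at least one falls by less than half.

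**The case against.** - **The comparison with 9.10.** A reader might infer that 9.10 contradicts Table 2, or that a clerical deviation must reach the sponsor sooner than a related death. The documents do not support this. The 5-day rule covers only emergencies that bear on life or physical well-being, it concerns a different kind of report, and its clock starts elsewhere. The two rules can coexist. What stands is that the protocol already regards 5 working days as workable for an urgent site report.
- **The tiering.** A reader might say that SAEs and AEs are treated alike. They are not: one time is a ceiling, the other a recommendation. What stands is that the ceiling is no shorter.
- **The near-miss deficiencies.** NOTE 1 can be read as moving them to the SAE row already, leaving the deficiency row for the rest. That is a fair reading, but Table 2 does not say so, and a site working from the table would see only the recommended time.
- **Other safeguards.** The medical monitor, direct reporting to the EC/IRB and deference to local rules are real, and local rules may be stricter. None of them sets an earlier site-to-sponsor time in these documents.
- **What the sponsor would do.** The documents contain no pause rule and no time for the sponsor to warn other sites. A faster report alone does not prevent a treatment. This stands in full and limits the claim.

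**Conclusion.** The point holds as a gap in safety reporting. Sites have up to 10 working days to report a related SAE, including a death, which is no shorter than the recommended AE time, and no passage sets a shorter limit. Table 2 and 11.1.2 NOTE 1 also need to be reconciled for device deficiencies with SAE potential.

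Per SAE reported at the limit, 0.55 to 1.38 further subjects would be expected to be treated before the sponsor knows. The figure of 1.38 (75%) is the top of the range: it needs 3 active sites at the stated rate and counts the site that already knows. A reader might infer that subjects will be exposed as a result. The figures show only that they can be, because they assume Poisson enrollment and a site that uses the full window, and the benefit of faster reporting depends on what the sponsor does next. This is a worthwhile, inexpensive correction. It bears on oversight during the trial and changes no statistical calculation.

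**What to change.** In Table 2 of section 11.2.1:

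1. Keep the SAE-to-sponsor limit mandatory. Make it shorter than the AE time and no longer than the 5 working days of 9.10, or any shorter period that local rules require.
2. Place device deficiencies that might have led to an SAE on the SAE row, with a reference to 11.1.2 NOTE 1, and keep the existing deficiency row for the others.

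The cost is an amendment to one table and somewhat faster site reporting for a small number of related events and near misses in at most 30 subjects. No endpoint, analysis or sample size changes.

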#### 12. Data Review Committees

There will be no Data Monitoring Committee or Clinical Events Committee as these are not required for a post-market study of a commercially available product.

## 13. Statistical Design and Methods

All statistical analyses will be performed using Statistical Analysis System (SAS) for Windows (version 9.4 or higher, SAS Institute Inc. Cary, NC) or other widely accepted statistical or graphical software.

Descriptive statistics will be used to present the data and to summarize the results. Continuous variables will be summarized with number of subjects (n), mean, standard deviation, median, and ranges. Categorical variables will be summarized by frequencies and percentages.

The sample size of this study is not based on power calculations of a statistical hypothesis test.

There are no pre-planned interim or subgroup analyses. Any post-hoc subgroup analyses will be exploratory in nature for the purpose of evaluating the safety and performance of the study device under various clinical conditions.

Due to the post-market and observational nature of the study, no imputation is planned for missing data in the primary and secondary endpoints, if any. All available data from enrolled subjects will be reported.

MDT18010ILSBA

Version 4.0

26-SEP-2019

Page 39 of 50

A detailed Statistical Analysis Plan (SAP) will be prepared prior to data analysis.

Any deviations from this analysis plan will be documented in the final clinical study report.

## 14. Ethics

## 14.1. Statement(s) of Compliance

This clinical investigation will be conducted in accordance with this CIP, the ethical principles that have their origin in the Declaration of Helsinki, as well as with ISO 14155:2011 (Clinical Investigation of Medical Devices for Human Subjects – Good Clinical Practice), the European Union Medical Device Regulation, and the International Conference on Harmonisation (ICH) of Technical Requirements For Registration of Pharmaceuticals For Human Use, ICH Harmonised Tripartite Guideline for Good Clinical Practice E6 (R1). This investigation will also be conducted per applicable local regulatory requirements and laws in which the study will be conducted.

The study will be compliant with ISO 14155:2011 with the following exceptions:

- The point of enrollment is defined as the insertion of the Emprint™ Ablation Catheter Kit with Thermosphere™ Technology into the EWC, rather than at the time of informed consent. Subjects will be approached to obtain written informed consent prior to any institution non-standard-of-care assessments or study specific data being collected. Subjects who provide study consent but then are determined to be ineligible prior to the insertion of the ablation catheter will be considered screen failures and documented as such in the database (see Section 8.2).
- For the purposes of this clinical study, AE definitions will be ISO 14155:2011 compliant with the following exception: only those AEs deemed to be related to the Emprint™ Ablation Catheter Kit with Thermosphere™ Technology, accessory devices, or study procedures will be captured and reported (see Section 11.1.1).

The principles of the Declaration of Helsinki have all been implemented by means of the patient informed consent process, EC approval, study training, clinical study registration, preclinical testing, risk benefit assessment, and publication policy.

Pediatric, legally incompetent, or other vulnerable subjects are not eligible for the study.

The clinical investigation will not begin until all necessary approvals/favorable opinions are obtained from the appropriate EC/IRBs or Regulatory Authority, as appropriate. Should an EC/IRB or regulatory authority impose any additional requirements, they will be followed.

Information regarding the study and study data will be made available via publication on clintrials.gov. Additionally, the results of this study will be submitted for publication in an appropriate journal.

No insurance or compensation will be provided to study subjects.

MDT18010ILSBA

Version 4.0

26-SEP-2019

Page 40 of 50

Medtronic maintains appropriate clinical study liability insurance coverage as required under applicable laws and regulations and will comply with applicable local law and custom concerning specific insurance coverage. If required, a clinical study insurance statement/certificate will be provided to the EC/IRB.

## 15. Study Administration

## 15.1. Monitoring

Authorized Medtronic representatives will conduct site initiation visits prior to first subject enrolled at a site. Site initiation visits include activities such as verification that training was conducted and documented.

Site monitoring visits will be conducted by an authorized Medtronic representative to inspect study data, subjects' medical records, and CRFs in accordance with current ISO 14155 and ICH GCPs and the respective local and national government regulations and guidelines (if applicable). The study investigator and the investigating site will permit authorized clinical research personnel and clinical monitors from Medtronic and/or designee(s) employed by Medtronic to review completed CRFs, EC/IRB decisions, and Investigator, clinical site records, and facilities relevant to this study at regular intervals throughout the study per the monitoring plan. Additionally, subject charts and clinical records will be requested and reviewed so that protocol adherence and source documentation can be verified.

The accuracy and quality of the data obtained from the investigator and maintained by the Sponsor will be confirmed through a structured program of clinical field auditing and internal review detailed in the monitoring plan. In instances where data protection regulations prohibit the direct examination of hospital records by the study Sponsor or designee(s), the Investigator will cooperate in a system of source data verification with the Sponsor. Monitoring may be performed with in person visits or remotely, when applicable.

To ensure the rights, safety, and welfare of study subjects are being maintained, the monitor will maintain assurance that all study staff are trained on the CIP and use of the study devices. If the monitor discovers that an investigator is not complying with the signed Investigator Statement, the investigational plan, applicable laws, or any conditions of approval imposed by the reviewing EC/IRB or Regulatory Authority, the monitor will report to the Sponsor and take such steps necessary to promptly secure compliance. If compliance cannot be secured, the investigator's participation in the investigation may be terminated.

Because there are no required medications for this study or other subject-generated reporting requirements, monitoring of subject compliance is not applicable to this study.

A minimum of 80% source data verification is required, though a higher percentage of verification will be attempted. All ICFs and eligibility criteria are required to be 100% source-data verified.

MDT18010ILSBA

Version 4.0

26-SEP-2019

Page 41 of 50

Authorized Medtronic representatives will also conduct site close-out visits. Site close-out visits include activities such as ensuring site files are complete and accurate, essential documents are collected, and reminding the site of their study closure responsibilities.

## 15.2. Data Management

This study will utilize an electronic database and eCRF. All data requested on the eCRF are considered required. Data points not collected and/or recorded will be considered deviations unless otherwise specified. No data points will be collected directly on the eCRF.

In order to accurately collect all information, subject worksheets may also be provided for study specific data (e.g. specific nodule and procedure data points, etc.) not found in the medical records and will be considered the source document.

The Principal Investigator must ensure the accuracy and completeness of the recorded data and then provide his/her electronic signature on the appropriate CRFs. The Investigator's signature for specific CRFs will be documented in compliance with local regulations. Changes to data previously submitted to the sponsor will require a new electronic signature by the Investigator to acknowledge/approve the changes.

Visual and/or computer data review will be performed to identify possible data discrepancies. Manual and/or automatic discrepancies will be created in the Oracle remote data capture (RDC) system and will be issued to the site for appropriate response. The site staff will be responsible for resolving all discrepancies in the database.

## 15.3. Direct Access to Source Data/Documents

The investigator(s)/institution(s) will permit inspection and study-related monitoring, audits, IRB/IEC review, and regulatory inspection(s), including direct access to source data/documents per applicable laws and regulations.

## 15.4. Confidentiality

All records identifying the subject will be kept confidential and, to the extent permitted by the applicable laws and/or regulations, will not be made publicly available.

Subject names will be kept confidential. Only the subject number will be recorded in the CRF, and if the subject name appears on any other document, it must be removed.

Study findings stored on a computer will be stored in accordance with local data protection laws. The subjects will be informed in writing that representatives of the sponsor, IRBs, or Regulatory Authorities may inspect their medical records to verify the information collected, and that all personal information

MDT18010ILSBA

Version 4.0

26-SEP-2019

Page 42 of 50

made available for inspection will be handled in strictest confidence and in accordance with local data protection laws.

Subjects will also be informed that information regarding the study that does not include subject identifiers will be posted on www.clinicaltrials.gov.

If the results of the trial are published, the subject's identity will remain confidential.

